#### **4.8 Vital Signs**

Vital signs (weight, systolic blood pressure, diastolic blood pressure, heart rate, and temperature) will be summarized at each scheduled assessment for the Safety Population. The change and percentage change from baseline will also be summarized for post-baseline assessments.

**Avapritinib**  
**Statistical Analysis Plan Study BLU-285-1303**

**4.9 Electrocardiograms**

Electrocardiogram overall interpretations (normal, abnormal not clinically significant [NCS], abnormal clinically significant [CS], and NE) and changes from baseline [expressed as improvement, no change, and deterioration] will be summarized by treatment group and scheduled visit for the Safety Population.

- Improvement = abnormal CS to abnormal NCS or normal, abnormal NCS to normal
- Deterioration = normal to abnormal NCS or CS, abnormal NCS to abnormal CS
- No change = normal to normal, abnormal NCS to abnormal NCS, abnormal CS to abnormal CS.

If an interpretation is missing for any patient, then an 'Unknown' category will be presented.

ECG parameters (heart rate, PR interval, QT interval, QRS interval, and QTcF) will be descriptively summarized by scheduled visit. The change and percentage change from baseline will be summarized for post-baseline assessments.

The proportion of patients with a QT interval and QTcF interval >450, >480 and >500 msec will be summarized. In addition, the proportion of patients with a change from baseline in QT interval and QTcF interval >30 and >60 msec will also be summarized.

Note, ECGs are not assessed following either continuation or crossover of treatment to avapritinib, following disease progression based on central review.

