- Abbreviations: AE = adverse event; C = cycle; CT = computed tomography; ctDNA = circulating tumor deoxyribonucleic acid; D = day; ECG = electrocardiogram; ECOG PS = Eastern Cooperative Oncology Group Performance Status; EORTC-QLQ-C30 = European Organisation for Research and Treatment of Cancer Quality of Life Questionnaire; EOT = End-of-Treatment; EQ-5D-5L = EuroQol 5 Dimension Questionnaire; F/U = follow-up; FACT-Cog = Functional Assessment of Cancer Therapy-Cognitive Function; GIST = gastrointestinal stromal tumor; IV = intravenous; MRI = magnetic resonance imaging; PD = progressive disease; PFS = progression-free survival; MRI = magnetic resonance imaging; PGI-C = Patients' Global Impression of Change; PGI-S = Patients' Global Impression of Severity; PK = pharmacokinetics; SAE = serious adverse event; ULN = upper limit of normal.
- a On days when study drug is to be administered in the clinic, all tests or procedures must be completed pre-dose at each study visit unless otherwise indicated. Additional safety tests (eg, hematology, ECG) may be performed whenever clinically indicated, at the Investigator's discretion. Whenever a test result is questionable, it should be repeated immediately.
  - b Patients receiving regorafenib who experience disease progression documented by central radiology review may be permitted to cross over to receive treatment with avapritinib after disease progression confirmed by central radiology review (see [Section 7.6](#)) and a washout period of 7 to 28 days after their last dose of regorafenib. At the first study visit after the washout period, the patient will complete the C1D1 assessment schedule except for the following tests, which are not required: PK blood sample and biomarker plasma sample. After patients cross over to treatment with avapritinib, ECGs will be performed following the same schedule as prior to cross over and AEs will only be assessed for their relationship to avapritinib.

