### **7.5.4**

## 7.6 Crossover From Regorafenib to Avapritinib

Patients who experience disease progression while receiving regorafenib (Arm B), as confirmed by central radiology review, may be offered the opportunity to cross over to the avapritinib treatment arm (Arm A).

Patients who cross over to avapritinib must complete a washout period of 7 to 28 days after their last dose of regorafenib and consent to cross over before starting treatment with avapritinib. At the first study visit after the washout period, cross over patients will complete the C1D1 assessment schedule except for the following tests, which are not required: PK blood sample and biomarker plasma sample. Otherwise patients who crossed over will follow the same schedule of assessments as on the main portion of the Protocol (except C1D15 or C2D15 visits, which are not required). After patients cross over to treatment with avapritinib, ECGs will be performed following the same schedule as prior to cross over and AEs will only be assessed for their relationship to avapritinib.

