## 7.7 Continuing Avapritinib After Disease Progression

Patients who experience disease progression while receiving avapritinib (Arm A), as confirmed by central radiology review, may be offered the opportunity to continue treatment with avapritinib if the following criteria are met:

- There are no symptoms or signs indicating clinical disease progression (including worsening of laboratory values).
- The patient is not experiencing rapid progression of disease or a progressive tumor requiring urgent alternative medical intervention at critical anatomical sites (eg, spinal cord compression).
- There has been no decline in ECOG PS

Patients randomized to Arm A must consent to continue avapritinib treatment after disease progression. This consent must be obtained after disease progression has occurred.

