**Avapritinib**  
**Statistical Analysis Plan Study BLU-285-1303**

**1. INTRODUCTION**

This statistical analysis plan (SAP) describes the statistical analyses and data presentations to be performed for Blueprint Medicines, Protocol No. BLU-285-1303 (amendment 3 dated 20 JUN 2019) ‘An International, Multicenter, Open-label, Randomized, Phase 3 Study of Avapritinib (BLU-285) vs Regorafenib in Patients with Locally Advanced Unresectable or Metastatic Gastrointestinal Stromal Tumor (GIST)’. It contains definitions of analysis populations, derived variables, and statistical methods for the analysis of efficacy and safety. It is to ensure that the data listings, summary tables, and figures which will be produced, and the statistical methodologies that will be used, are complete and appropriate to allow valid conclusions regarding the study objectives.

The SAP will be finalized and approved prior to the clinical database lock for the final analysis, when approximately 264 progression free survival (PFS) events are reached. The analyses of safety, efficacy and pharmacokinetics will include all data collected in the database through the data cutoff date.

A follow-up analysis for overall survival will be conducted when approximately 264 deaths have been observed. Additional data collected after the database lock from the primary analysis of the study will be prepared as an addendum to the study report per regulatory or scientific need.

Selected analyses from this SAP will be performed for the Independent Data Monitoring Committee (IDMC) to review accumulated data from the study. Further details are described separately in the IDMC Charter.

Analysis of pharmacokinetics (PK) is outside the scope of this SAP and will be addressed separately.

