## **Avapritinib**

### **Statistical Analysis Plan Study BLU-285-1303**

- regorafenib to avapritinib (“rego to ava”) – Data collected during the extended study treatment period only from patients randomized\* to regorafenib. During this period, patients are treated with avapritinib after crossing over from regorafenib.

\*For analyses using the Safety Population, patients will be grouped based on the study drug actually received during the main study treatment period rather than the study drug they were randomized to.

Safety, laboratory, exposure, compliance, dose modification, concomitant medications, and major protocol deviation analyses will be presented using the 4 groups above.

Efficacy analyses will be presented using 2 groups (avapritinib, regorafenib).

Analysis populations, patient dispositions, baseline or demographic characteristics, patients by country by site, medical history, and prior therapies for the underlying malignancy will be presented using 3 groups (avapritinib, regorafenib, total).

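### SAP 4.9 says no ECGs follow crossover or continuation, but the protocol requires them after crossover and exempts no continuing patient, so extended-period ECG and QTcF summaries could be omitted

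*SAP*

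**What the plan says.** **SAP 4.9** plans ECG interpretations and parameters by visit, the proportions of patients with QT and QTcF above 450, 480 and 500 msec, and the proportions with increases above 30 and 60 msec. It then adds that "ECGs are not assessed following either continuation or crossover of treatment to avapritinib", referring to treatment after centrally reviewed progression.

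**Protocol 7.6** says: "After patients cross over to treatment with avapritinib, ECGs will be performed following the same schedule as prior to cross over". Note b to protocol Table 2 repeats it: "ECGs will be performed following the same schedule as prior to cross over and AEs will only be assessed for their relationship to avapritinib".

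**Protocol 7.7**, on Arm A patients who "may be offered the opportunity to continue treatment with avapritinib if the following criteria are met", does not mention ECGs.

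**SAP 3.2.7** defines four reporting groups. 'rego to ava' holds only extended-period data, and 'ava overall' combines main and extended periods for patients randomized to avapritinib. It states: "Safety, laboratory, exposure, compliance, dose modification, concomitant medications, and major protocol deviation analyses will be presented using the 4 groups above".

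**SAP section 6** reports no change from the protocol's planned analyses.

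**The concern.** The SAP tells the programming team that a set of data does not exist, while the protocol instructs sites to collect it. A team working from SAP 4.9 would probably build no ECG output for the extended treatment period. Crossover patients are a distinct avapritinib-exposed group, since they start the drug 7 to 28 days after their last regorafenib dose. QTcF is also a measure the trial takes seriously: a value above 450 msec excludes a patient at entry (protocol 5.3), and the SAP sets categorical thresholds for it. At stake is the description of ECG safety on avapritinib after crossover or progression, not any efficacy inference.

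**Working it through.** The point rests on comparing texts. There is no figure in the plan to reproduce.

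**1. Are ECGs collected after crossover?** Yes.
- Protocol 7.6 and Table 2 note b both say so.
- At the first visit after washout the patient repeats the C1D1 assessments except for tests "which are not required: PK blood sample and biomarker plasma sample". The C1D1 ECG is not among the waived tests.
- Thereafter, "Otherwise patients who crossed over will follow the same schedule of assessments as on the main portion of the Protocol". The exceptions are the C1D15 and C2D15 visits, for which Table 2 has no ECG entry, so waiving them removes no ECG.

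**2. Are ECGs collected on continuation?** By implication only. Protocol 7.7 neither requires nor waives them. The 12-lead ECG row of Table 2 covers the C7-EOT column and the EOT visit, and no footnote exempts patients treated beyond progression.

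**3. Could this be a declared change or a version mismatch?** The SAP identifies its source as "Protocol No. BLU-285-1303 (amendment 3 dated 20 JUN 2019"), and section 6 declares no departure. Protocol 10.5.4.3 plans ECG summaries over time without excluding the post-crossover period.

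**4. Does the SAP agree with itself?** No.

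| SAP location | Treatment of extended-period data |
|---|---|
| 3.2.7 | Safety analyses use four groups, two of which include the extended period |
| 4.7 | ECG data are named as safety data; all safety data are summarized by treatment group |
| 4.9 | ECGs said not to be assessed after continuation or crossover |
| 4.12 | ECOG PS said to be captured after continuation or crossover, and summarized |

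The 4.12 note is the counterpart of the 4.9 note with the opposite content. Read together, they suggest that the author of 4.9 meant no extended-period ECG output. Under that reading the 'rego to ava' ECG column is empty and 'ava overall' adds nothing to 'ava'.

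**5. How many patients?** Only Arm B patients can cross over, and Arm B has about 230 (protocol 5.1). The range is therefore 0 to about 230, plus an unstated number of continuing Arm A patients. Neither document gives an expected rate of crossover or continuation, so no point estimate follows.

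**The case against.** The strongest reply is that the 4.9 note is a mistaken remark about data collection and not an exclusion rule. SAP 3.2.7 and 4.7 are operative text and would put any ECG in the database into the right group. SAP 3.2 also sends all relevant patient data to listings. This stands in part: omission is the likely result of the note, not something the SAP orders.

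The loss is also limited. The randomized main-period ECG comparison is unaffected, and so are crossover patients' ECGs taken while on regorafenib. Clinically significant findings are still reported as adverse events (protocol 7.2), and adverse events are summarized for the extended period (SAP 3.2.7, 4.7.1). Post-crossover ECGs have no concurrent control, and the protocol makes categorical QTcF analysis optional. All of this is correct, and it limits how serious the point is. It does not remove the contradiction, because adverse event reports do not replace the threshold tables that the SAP itself plans.

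Two stronger readings are tempting but unsupported.

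- **Size.** A reader might infer that a third to nearly half of all avapritinib-exposed patients would lack summarised ECGs, by assuming that 50% to 85% of Arm B crosses over: 0.50 × 230 = 115 and 115/345 = 33%; 0.85 × 230 = 195.5 and 195.5/425.5 = 46%. The 50% has no source. The 85% is the share of placebo patients who took open-label drug in the earlier regorafenib trial (protocol 1.1.2), where median PFS on placebo was 0.9 months, against about 5 months assumed for this control arm. Crossover here requires centrally confirmed progression. At the 264-event analysis, 196 crossovers would leave at most 264 − 196 = 68 PFS events for Arm A. Under the plan's own assumptions (exponential PFS, medians 5 and 5/0.67 = 7.5 months, 230 per arm, 18-month accrual, dropout ignored), Arm B contributes about 146 to 148 of the 264 events, including deaths.
- **Continuation.** A reader might infer that the protocol explicitly requires ECGs on continuation as it does on crossover. Only the crossover requirement is explicit; the other is implied by Table 2.

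**Conclusion.** SAP 4.9 is wrong as written. It contradicts explicit current protocol text on ECGs after crossover, it conflicts with the Table 2 schedule for patients who continue, and it is inconsistent with SAP 3.2.7 and 4.7. None of this is declared in SAP section 6. If the note is followed, extended-period ECG and QTcF summaries could be omitted for 0 to about 230 crossover patients and for continuing Arm A patients, although the data are collected. The conclusion about the consequence assumes that sites follow the protocol and that programmers follow the note in preference to the general rules. The contradiction itself depends on neither assumption, nor on any crossover rate. Primary and key secondary analyses, the main-period ECG comparison and adverse event reporting are not affected.

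**What to change.** Reconcile SAP 4.9 with protocol 7.6 and Table 2:

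- Remove the note from SAP 4.9.
- State that ECG interpretations, the QT and QTcF thresholds, and the changes from baseline will also be summarised for 'rego to ava' and 'ava overall'.
- Name the baseline for each. 'rego to ava' uses the rebaseline defined in SAP 3.2.5. 'ava overall' uses the original baseline, because SAP 3.2.5 says patients randomized to avapritinib are not rebaselined on continuation.
- State explicitly how ECGs in continuing Arm A patients are handled, since protocol 7.7 is silent.
- If leaving these summaries out is intended, list the departure in SAP section 6 and justify it there.

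The cost is SAP wording and extra table columns. No new data collection is needed.

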**4.10 Physical Examination**

Any abnormal, clinically significant physical examination results captured at screening will be treated as either medical history or adverse event data, as appropriate. Data will be listed for patients who have physical examinations performed.

**4.11 Basic Neurological Assessment**

Basic neurological assessment results at screening will be summarized.

**4.12 ECOG Performance Status**

ECOG PS will be summarized by scheduled visit. The number and percentage of patients with each response will be summarized.

Note, ECOG PS is also scheduled to be captured following either continuation or crossover of treatment to avapritinib, following disease progression based on central radiological assessment. These scheduled assessments will also be summarized.

## **5. INTERIM ANALYSES**

No interim analysis is planned for the primary endpoint of this study. An interim analysis of OS is planned at the time of final analysis when superiority of the PFS and ORR are established.

The OS interim analysis will be performed at the time of the final analysis of PFS and ORR for which superiority is demonstrated. The alpha for the interim analysis of the OS will follow the O'Brien-Fleming boundary method. The amount of alpha spent on OS at the time of the final PFS analysis will be specified according to the actual proportion of deaths observed at the time of the database lock regardless of whether the exact targeted number of PFS events has occurred at the lock. The exact amount of alpha spending at the interim analysis will be calculated using the alpha spending function developed by Lan and DeMet. OS will be analyzed when superiority is demonstrated for both PFS and ORR. The OS will also be analyzed at the follow-up when 264 events (deaths) occur, using the remaining unspent alpha.

**6. CHANGES TO PLANNED ANALYSES FROM THE PROTOCOL**

There is no change to planned analyses from the protocol.

## **7. APPENDICES**

### **7.1 Data Imputation Guidelines**

No imputation will be made for completely missing date unless otherwise specified. General imputation rules mentioned below apply to partially missing or impossible dates:

- If the stop date is not missing, and the imputed start date is after the stop date, the start date will be imputed by the stop date
- If the start date is not missing, and the imputed stop date is before the start date, then the imputed stop date will be equal to the start date
- Any imputed dates need to be logical. For example, last dose date should not be later than death date.

When imputation rules in subsequent sections contradicts the general rule, always follow the general rule.

#### **7.1.1 Adverse Event Date Imputation**

Follow the general rule specified in [Section 7.1](#).

##### **Incomplete Start Date:**

*Missing day, month, and year*

- No imputation will be made; the corresponding AE will be included.

*Missing day and month*

- If the year is the **same** as the year of the first dose date, then impute day and month as the day and month of the first dose date
- If the year is **prior to** the year of the first dose date, then impute day and month as 31 Dec
- If the year is **after** the year of the first dose date, then impute day and month as 01 Jan.

*Missing day only*

- If the month and year are the **same** as those of the first dose date, then impute day as the day of the first dose date
- If either the year of partial date is **before** the year of the first dose date, or the years are the same, but the month of partial date is **before** the month of the first dose date, then impute day as last day of the month
- If either the year of partial date is **after** the year of the first dose date, or the years are the same, but the month of partial date is **after** the month of the first dose date, then impute day as first day of the month.

**Avapritinib**  
**Statistical Analysis Plan Study BLU-285-1303**

**Incomplete Stop Date:**

*Missing day, month, and year*

- No imputation will be made.

*Missing day and month*

- If the year is the **same** as the year of the last dose date, then impute day and month as the day and month of the last dose date
- If the year is **prior to** the year of the last dose date, then impute day and month as 31 Dec
- If the year is **after** the year of the last dose date, then impute day and month as 01 Jan.

*Missing day only*

- If the month and year are the **same** as those of the last dose date, then impute day as the day of the last dose date;
- If either the year of partial date is **not the same as** the year of the last dose date, or the years are the same, but the month of partial date is **not the same as** the month of the last dose date, then impute day as last day of the month.

**7.1.2 Concomitant Medication Date Imputation**

Follow the general rules specified in [Section 7.1](#) and rules in [Section 7.1.1](#).

**7.1.3 Prior Therapies Date Imputation**

Follow the general rule specified in [Section 7.1](#).

For start date partial as month and year are available, then impute day as '01'. *E.g.* impute partial date of 'DEC2013' as '01DEC2013'.

For start date partial as year only is available, then impute day and month as '01JAN'. *E.g.* impute partial date of '2013' as '01JAN2013'.

For end date partial as month and year are available, then impute day as last day of the month. *E.g.* impute partial date of 'JUN2013' as '30JUN2013'.

For end date partial as year only is available, then impute day and month as the last day of the year. *E.g.* impute partial date of '2013' as '31DEC2013'.

If the imputed starting date is earlier than initial diagnosis date, it should be set as the initial diagnosis date. No overlap between the exposure to prior therapies and study drug will be allowed and any overlap of exposure will be queried at data review stage. The end date of prior therapies will be imputed to first dose date of study drug – 15 if there is overlap due to imputation of partial dates. When there are multiple lines of prior therapies, the end date of

**Avapritinib**  
**Statistical Analysis Plan Study BLU-285-1303**

prior therapies will be imputed to first dose date of the subsequent line of therapy -1 if there is overlap due to imputation of partial dates. If the end year for one prior therapy is the same as the start year for the next prior therapy, impute Jun 30 and Jul 1 of that year for the end and start days if missing months and days. If the end year and month for one prior therapy is the same as the start year and month for the next prior therapy, impute 15th and 16th of that year and month for the end and start days if missing days.

**7.1.4 Death Date Imputation**

- If death date is completely missing, will use latest alive date + 1
- If both month and day are missing, then use the first date (01 JAN) of the year, or latest alive date + 1, whichever is later
- If only day is missing, then use the first day of the month, or latest alive date + 1, whichever is later.

**7.1.5 Post-Therapies Date Imputation**

Follow the general rule specified in [Section 7.1](#).

**7.1.6 Other Imputations**

Follow the general rule specified in [Section 7.1](#).

## **7.2 Table, Listing, and Figure Format**

In the top left portion of each table/listing, a *table/listing number* followed by the *title* of the table/listing will be presented. After the title line, optional *sub-title* or *population* information can be presented. Horizontal lines will appear before and after the column heading of the table/listing. *Footnotes* will be put under the main body of text at the bottom of the page.

The *sponsor name*, *protocol number*, programmer user identification, status of the table/listing (i.e. draft or final) and *SAS program name* will appear bottom left in a string and the *page number* will appear on the bottom right corner of each table/listing. The *date and time of creation* of table/listing will appear bottom left under the sponsor name. The source listing number will appear bottom left.

A *landscape layout* is for both table and listing presentations for post-text tables. A *portrait* layout is for in text table.

The *left and right margins* of all tables and listings will be a minimum of 2.1 cm from the left and 1.9 cm from the right. The *top and bottom margins* will be a minimum 2.92 cm. *Header and footer* will be both 1.27 cm.

There is no special requirement of *font type and size*, but an *8-point* font size for tables and *7or 8-point* for listings is proposed using *Courier New* font. A maximum SAS line size = 141 and page size = 44 for *8-point* font size, and line size = 161 and page size = 50 for *7-point* will be used to fit on both United Kingdom and US paper sizes.

In a listing, in the case that a patient's record has been continued to the next page, an appropriate identification (e.g. the patient identification number) must be presented at the beginning of that page.

